Study Protocol and Statistical Analysis Plan

Evaluation of Medical Education With Telemedicine on Technical Knowledge and Quality of Care for Patients With Hyperglycemia and Diabetes in the Hospital Setting – A Multicenter Randomized Clinical Trial

NCT Number:

Pending

Document Date:

May 31, 2025

1. Introduction and Rationale

Diabetes mellitus is a major global health challenge with a growing burden in both outpatient and inpatient settings. In Brazil, recent data reveal a high prevalence of diabetes. A study conducted across six Brazilian capitals among public university employees aged 35 to 74 years found a prevalence of 20%, with approximately half of the cases previously undiagnosed.

It is estimated that 22% of all hospitalized patients have diabetes. In the United States, hospitalizations account for nearly half of the \$174 billion in total annual medical expenditures related to diabetes. Each year, 1.6 million new cases are diagnosed in the U.S., with an overall prevalence of 23.6 million individuals—7.8% of the population—of whom approximately one-quarter remain undiagnosed.

Hospital admission rates for patients with diabetes range from 14% to 20%, particularly within the first 30 days following discharge. Major risk factors for readmission include lower socioeconomic status, race/ethnicity (e.g., Hispanic, African American, Native American, and Asian American), comorbid conditions, and recent hospitalizations.

Approximately 30% of patients with two or more hospitalizations account for more than 50% of all admissions and related costs. Although there is no universally accepted protocol to prevent readmissions, several effective strategies have been reported. These include targeted interventions for high-risk patients with poor glycemic control and the implementation of transitional care models.

Glycemic disturbances—such as hyperglycemia, hypoglycemia, and glucose variability—in hospitalized patients have been associated with adverse outcomes, including prolonged hospital stays, increased morbidity, and mortality. Evidence from clinical practice also highlights the relevance of physician knowledge and the role of specialized diabetes care teams as important predictors of improved glycemic control and reduced hospital length of stay.

Telemedicine has emerged as a valuable tool in diabetes management, especially through remote monitoring, communication platforms, and therapeutic adjustments. However, most studies involving telemedicine focus on outpatient or primary care contexts.

Given the severity of diabetes-related complications, the economic impact of hospitalizations, the persistently high readmission rates, and the need to strengthen medical knowledge for inpatient diabetes care, this study proposes a structured, telemedicine-based educational intervention. The objective is to evaluate its effectiveness in improving medical knowledge, insulin prescription quality, and the prevention and management of glycemic extremes during hospitalization.

2. Primary and Secondary Objectives

Primary objective:

To evaluate the impact of a structured educational intervention via telemedicine on internal medicine residents' knowledge regarding inpatient hyperglycemias.

Secondary objectives:

To assess the effect of the intervention on the quality of insulin prescriptions and capillary blood glucose monitoring.

To evaluate the effect on the occurrence of hypoglycemia and hyperglycemia during hospitalization.

To compare the length of hospital stay between the intervention and control groups.

3. Study Design

This was an open-label, multicenter, randomized clinical trial conducted at university hospitals located in southern Brazil. Internal medicine clinical teams were block-randomized using stratified allocation by center to ensure balance between groups.

The intervention group received a 30-minute online theoretical lecture on hospital hyperglycemia and participated in a 30-day telemedicine-based continuing education program delivered via a messaging platform. The control group continued standard clinical activities without any educational intervention.

Data collection occurred in two phases: a pre-post knowledge assessment using a validated questionnaire, and a retrospective chart review of hospitalized patients cared for by the participating teams.

4. Intervention

Residents in the intervention group received a 30-minute online theoretical lecture on inpatient hyperglycemia, followed by daily educational content for 30 days via a messaging application. Materials included short videos, texts, and clinical guidance on diabetes and hospital glycemic management.

The control group received no educational content and maintained routine clinical duties.

5. Inclusion and Exclusion Criteria

Inclusion criteria:

Internal medicine residents assigned to clinical teams at participating hospitals.

Exclusion criteria:

Residents on leave during the intervention period.

Teams supervised by endocrinologists.

Residents who declined participation.

6. Outcome Measures (Primary and Secondary)

Primary outcome:

Change in medical knowledge on inpatient hyperglycemia, assessed through a validated questionnaire before and after the intervention.

Secondary outcomes:

Quality of glucose monitoring and insulin prescribing.

Incidence of hyperglycemia (>180 mg/dL) and hypoglycemia (<70 mg/dL).

Length of hospital stay

7. Sample Size Calculation

Based on previous data showing 46.44% accuracy in key knowledge items, and assuming an increase to 80% after the intervention, with 80% power and a 5% significance level, a minimum of 62 completed questionnaires (including both pre- and post-intervention assessments) was required.

8. Statistical Analysis Plan

Categorical variables were described as frequencies and percentages. Continuous variables were expressed as means and standard deviations or medians and interquartile ranges, based on normality (Shapiro-Wilk test).

Between-group comparisons were made using Student's t-test or the Mann-Whitney U test for continuous variables, depending on distribution. Categorical variables were analyzed using Pearson's chi-square test or Fisher's exact test, as appropriate. Logistic regression analysis was performed to identify independent predictors, including variables with clinical relevance or $p < 0.20$ in the univariate analysis. Statistical analyses were conducted using IBM SPSS Statistics for Windows, Version 29.0 (IBM Corp., Armonk, NY, USA). A two-sided p -value < 0.05 was considered statistically significant.

9. Ethical Considerations

All participating physicians provided informed consent. Data were collected with institutional authorization and approval by the local ethics committee. Confidentiality and privacy were strictly maintained for all participants and patient information.

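### Clinical teams were randomised, but every planned test treats residents and patients as independent, so the 5% error rate is not kept

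*Combined protocol and SAP*

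**What the plan says.** Section 3 (Study Design) sets the unit of randomisation: "Internal medicine clinical teams were block-randomized using stratified allocation by center to ensure balance between groups". Outcomes are then measured one level down:

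- **Primary outcome (Section 6):** "Change in medical knowledge on inpatient hyperglycemia, assessed through a validated questionnaire before and after the intervention". The people assessed are, per Section 5, "Internal medicine residents assigned to clinical teams at participating hospitals".
- **Secondary outcomes:** monitoring and prescribing quality, hyper- and hypoglycaemia, and length of stay. The patient data come from "a retrospective chart review of hospitalized patients cared for by the participating teams" (Section 3).

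Section 8 compares groups by Student's t-test or "the Mann-Whitney U test for continuous variables, depending on distribution", by Pearson's chi-square or Fisher's exact test for categorical variables, and by a logistic regression for independent predictors. It names no random effect, generalised estimating equation (GEE), cluster-robust variance, team-level summary or adjustment for centre. Section 7 gives a minimum of 62 questionnaires, with no ICC, team size, number of teams or design effect.

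**The concern.** The listed tests take each resident or patient as a separate, independent piece of information about the intervention. Under team randomisation they are not. Residents on a team share a supervisor and a working environment. Patients on a team share prescribers, and prescribing is what the intervention is meant to change.

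The protocol itself gives reason to expect similarity within teams. The Introduction names physician knowledge and specialised diabetes teams as predictors of glycaemic control and length of stay. Section 5 excludes teams with an endocrinologist as supervisor.

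With positive within-team correlation, the true variance of the difference between arms is larger than these tests estimate, so p-values (and any confidence intervals reported) are too optimistic. Every between-group comparison is exposed. The patient outcomes are the most exposed, because each team is likely to contribute many patients. The risk is that an ineffective programme is reported as improving care.

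**Working it through.** **1. The plan's own sample size.** Inputs from Sections 7 and 8: 46.44% versus 80%, 80% power, two-sided 5%. An equal allocation ratio is assumed.

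- Arcsine formula: n per group = 2 × [(1.96 + 0.8416)/h]², with h = 2·asin√0.80 − 2·asin√0.4644. This gives 30.7, rounded up to 31, so **62 in total**.
- Pooled-variance formula: 31.2 per group, rounded up to 32, so 64 in total. Power with 31 per group is 79.7%.

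The figure of 62 is therefore what two independent, individually randomised groups would need. That implies a design effect of 1.

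**2. Error rate when team is ignored.** With m observations per team, the design effect is DE = 1 + (m − 1) × ICC. The true two-sided error of a nominal 5% test is 2 × [1 − Φ(1.96/√DE)]. Neither m nor ICC is in the documents, so both are assumed ranges. Example for m = 20, ICC 0.05: DE = 1 + 19 × 0.05 = 1.95; 1.96/√1.95 = 1.404; error = 16.0%.

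| Unit | m | ICC | DE | Error, formula | Error, simulated t-test |
|---|---|---|---|---|---|
| Residents | 4 | 0.01 | 1.03 | 5.3% | 5.3% |
| Residents | 4 | 0.05 | 1.15 | 6.8% | 6.7% |
| Residents | 4 | 0.10 | 1.30 | 8.6% | 8.7% |
| Residents | 4 | 0.20 | 1.60 | 12.1% | 12.0% |
| Patients | 20 | 0.01 | 1.19 | 7.2% | 7.1% |
| Patients | 20 | 0.02 | 1.38 | 9.5% | 10.0% |
| Patients | 20 | 0.05 | 1.95 | 16.0% | 17.2% |
| Patients | 20 | 0.10 | 2.90 | 25.0% | 25.4% |
| Patients | 30 | 0.02 | 1.58 | 11.9% | 12.0% |
| Patients | 30 | 0.05 | 2.45 | 21.1% | 21.6% |
| Patients | 30 | 0.10 | 3.90 | 32.1% | 32.6% |

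Simulations used clustered normal data with no true effect: 8 teams per arm for residents and 6 for patients. A t-test on team means stayed between 4.7% and 5.5% in all scenarios run.

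**3. Allowing for stratification by centre.** When teams are balanced within centre, centre differences cancel from the comparison but remain in the naive error term. Write ρT for the share of variance between teams within centre and ρC for the share between centres. The ratio of true to assumed variance is then approximately mρT + (1 − ρT − ρC) = 1 + (m − 1)ρT − ρC. Simulations used 4 centres with 2 teams per arm in each:

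- Residents, m = 4, ρT = ρC = 0.10: 1 + 0.30 − 0.10 = 1.20, error 7.4% (simulated 7.3%).
- Residents, m = 4, ρT = 0.05, ρC = 0.15: 1 + 0.15 − 0.15 = 1.00, error 5.0% (simulated 5.9%).
- Patients, m = 20, ρT = ρC = 0.025: 1 + 0.475 − 0.025 = 1.45, error 10.4% (simulated 10.5%).
- Patients, m = 20, ρT = ρC = 0.01: 1 + 0.19 − 0.01 = 1.18, error 7.1% (simulated 6.8%).

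**4. Power.** At m = 4 and ICC 0.05, DE = 1.15. The pooled formula then needs 31.2 × 1.15 = 35.9, so 36 per group and 72 in total. With 31 per group, power falls from 79.7% to 73.7%. Over m = 3 to 6 and ICC 0.01 to 0.20, the required total runs from 64 to 126 and power at 31 per group from 78.9% to 49.0%.

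**The case against.** Nothing elsewhere in the document supplies the missing adjustment. The case on the other side concerns size.

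- **The inflation is conditional.** With zero within-team correlation the tests keep 5%, and the documents give nothing from which to estimate the correlation. This stands. The same silence means nobody can show from the plan that the effect is negligible.
- **The primary outcome is a change score.** Differencing removes stable differences between teams, so its ICC may be low. At ICC 0.01 with 4 residents per team, the error is about 5.3%. This stands as a limit on the primary outcome; it does not carry over to outcomes with many patients per team.
- **Leaving out centre works in the conservative direction.** This is correct, and the ICCs in the main table should be read as wholly within centre. Where centre variation is large relative to team variation, it removes much of the excess for residents (step 3). It does not rescue the patient outcomes: with 20 patients per team the simulated error stayed above 5% whenever there was any positive team correlation.
- **Wording of Section 8.** It mentions p-values and plans no confidence intervals explicitly. Its logistic model could admit centre as a clinically relevant variable, although centre is not named. Both points are fair, but neither brings team into any analysis.

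**Conclusion.** The concern holds. The analysis in Section 8 does not match the randomisation in Section 3, and this applies to every between-group test.

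Its size rests on assumed team sizes and within-centre ICCs. For the knowledge score, the true error plausibly lies anywhere from close to 5% up to about 12% (4 residents per team, ICC up to 0.20). For the patient outcomes, it is about 7% to 25% with 20 patients per team (ICC 0.01 to 0.10), and up to about 32% with 30 per team at ICC 0.10. Some of this would be offset if much of the correlation lies between centres.

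This must be fixed before results are relied on, most clearly for prescribing quality, glycaemic events and length of stay.

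**What to change.** Replace the individual-level between-group tests in Section 8 with analyses that respect the team:

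- **Knowledge score:** a linear mixed model for the post-intervention score, with arm, centre and baseline score as fixed effects, a random intercept for team, and small-sample degrees of freedom.
- **Binary patient outcomes:** a mixed logistic model, or GEE clustered on team with a small-sample variance correction, adjusted for centre.
- **Length of stay:** the same structure on a log or rank scale.
- **If teams are few:** a team-level summary analysis, or a permutation test that re-randomises teams within centre. State in advance the number of teams below which this applies.

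Report the number of teams per arm, team sizes and ICCs. Restate Section 7 with a design effect, and say whether 62 means 62 residents or 31 residents measured twice. In the second case (about 15 per arm), between-arm power is about 48% even before clustering.

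The cost is SAP text and modest extra analysis. Team and centre are known from randomisation, so no new data are needed. Intervals will be wider and some power will be lost. Because the document is written in the past tense, the change should be dated and, if results have already been seen, disclosed as a re-analysis.

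### The tests planned for hypo- and hyperglycaemia carry no term for the randomised team or for centre, so if run on patients or readings they will generally overstate precision

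*Combined protocol and SAP*

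**What the plan says.** - **Allocation (Section 3):** "Internal medicine clinical teams were block-randomized using stratified allocation by center to ensure balance between groups".
- **Source of the glycaemic data (Section 3):** "a retrospective chart review of hospitalized patients cared for by the participating teams". Patients are therefore nested in the randomised teams.
- **Outcome (Section 6):** "Incidence of hyperglycemia (>180 mg/dL) and hypoglycemia (<70 mg/dL". No unit, denominator or observation window is given. The matching objective in Section 2 reads: "To evaluate the effect on the occurrence of hypoglycemia and hyperglycemia during hospitalization".
- **Analysis of continuous measures (Section 8):** "Between-group comparisons were made using Student's t-test or the Mann-Whitney U test for continuous variables, depending on distribution".
- **Analysis of yes/no and other categorical measures (Section 8):** the plan names chi-square or Fisher's test, chosen by suitability.
- **Regression (Section 8):** "Logistic regression analysis was performed to identify independent predictors". Its covariates are picked on clinical grounds or by a univariate p below 0.20.
- **Related secondary outcomes (Section 6):** "Quality of glucose monitoring and insulin prescribing", and length of hospital stay.

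The documents do not mention clustering, a team or centre effect, repeated readings within a patient, or exposure time. They do not state the number of teams, centres, or patients per team.

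**The concern.** Each test in Section 8 treats the observations given to it as independent. Patients of one team share prescribers and habits of glucose management, so their outcomes may be more alike than those of patients of different teams in the same centre. The between-arm comparison then rests on less information than the patient count suggests, and a test that ignores this can declare differences too readily. Pooled readings would add a second layer, because readings from one patient are also correlated.

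At stake is the trial's claim about patients: whether teaching residents changes how often low and high glucose occurs. These outcomes are secondary, but they carry the step from knowledge to care.

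A smaller point follows from the missing unit. If the outcome is a yes/no per patient, an event is recorded only when a test was done. More tests or more days give more chances to record one. Monitoring quality and length of stay are themselves compared between arms, so those chances may differ by arm.

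**Working it through.** **1. The plan's own figure.** The only sample-size figure is 62 questionnaires (46.44% vs 80%, 80% power, two-sided 5%). By the arcsine formula, h = 2·asin(√0.80) − 2·asin(√0.4644) = 0.715, and n = 2·((1.960 + 0.842)/0.715)² = 30.7. That is 31 per group and 62 in total, so the figure reproduces. It treats questionnaires as independent and concerns knowledge only. No figure is given for the glycaemic outcomes.

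**2. Team clustering, patient as unit.** The documents give no inputs, so these are assumptions: m = 10-30 patients per team, and ICC = 0.01-0.10, meaning the correlation left within centre. Design effect DE = 1 + (m − 1)·ICC. True size of a nominal 5% test = 2·(1 − Φ(1.96/√DE)). With no centre variance:

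| m | ICC 0.01 | 0.02 | 0.05 | 0.10 |
|---|---|---|---|---|
| 10 | DE 1.09, 6.0% | 1.18, 7.1% | 1.45, 10.4% | 1.90, 15.5% |
| 20 | 1.19, 7.2% | 1.38, 9.5% | 1.95, 16.0% | 2.90, 25.0% |
| 30 | 1.29, 8.4% | 1.58, 11.9% | 2.45, 21.1% | 3.90, 32.1% |

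Simulation with 8 teams per arm agrees. At m = 20 and ICC 0.05, chi-square on a yes/no gave 16.6%, the t-test on a continuous per-patient measure 15.8%, and Mann-Whitney 17.0%. A t-test on team means held 4.8-5.3% with 4, 8 or 20 teams per arm.

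**3. Effect of omitting centre.** Stratified allocation balances centre between arms, but an unadjusted test keeps the between-centre variance in its standard error. If centre explains a share c of variance and arms are balanced within centre, the variance ratio is about (1 − c)·DE.

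- m = 10, ICC 0.01: c = 0.05 gives 0.95 × 1.09 = 1.036, size 5.4%. c = 0.10 gives 0.981, size 4.8%.
- m = 20, ICC 0.05: c = 0.05 gives 1.853, size 15.0%. c = 0.10 gives 1.755, size 13.9%.
- m = 30, ICC 0.10: c = 0.10 gives 3.51, size 29.5%.

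**4. Pooled readings.** With an assumed 28 readings per patient and within-patient correlation 0.1 to 0.3, DE = 1 + 27 × 0.1 = 3.7 up to 1 + 27 × 0.3 = 9.1. The size is 31% to 52% before any team effect.

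**5. Detection, only if the outcome is a yes/no per patient.** With n readings and a share q out of range, P(any) = 1 − (1 − q)ⁿ for independent readings, or the beta-binomial equivalent for within-patient correlation ρ. Assume no true effect, a 7-day stay and 3 tests a day as reference (n = 21), with ρ from 0 to 0.40.

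| Comparison with n = 21 | Low readings, q = 2% | High readings, q = 20-40% | High readings, q = 5% |
|---|---|---|---|
| 4 tests/day, 7 days (n = 28) | RR 1.25 (ρ = 0), 1.15 (0.10), 1.09 (0.40) | 1.00-1.05 | 1.08-1.16 |
| 3 tests/day, 5 days (n = 15) | 0.76-0.90 | 0.94-1.00 | 0.81-0.91 |
| 4 tests/day, 5 days (n = 20) | 0.96-0.99 | – | – |

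More testing and a shorter stay pull in opposite directions and can nearly cancel. A per-patient proportion of readings out of range does not rise mechanically with n. With 21 vs 28 readings its mean was 2.0% in both arms.

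**The case against.** **A Section 8 test can respect the randomisation.** A reader might infer that the listed tests are invalid whatever the unit. They are not: a t-test or Mann-Whitney on one summary per team is a Section 8 test and holds its size, as step 2 shows. What stands is narrower. No section says that team summaries are used, and use on patients or readings ignores the team.

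**Inflation is not certain.** A reader might also infer that p-values must be too small. Step 3 shows that omitted centre variance works the other way and can cancel or slightly reverse the effect when teams are small and the ICC is low. This removes the bottom of the range but not the middle or top.

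**The detection point is doubly conditional.** It needs a yes/no unit, which the word for occurrence in Section 2 suggests but does not fix. It also needs testing or stay to differ by arm, and monitoring quality is undefined and need not mean tests per day. This objection stands, so the point is only a secondary note. Nor do the documents support an unconditional claim that hyperglycaemia escapes it. That depends on high readings being common, and Section 3 states no restriction of the chart review to patients with diabetes.

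**Scope.** The missing team term affects all of Section 8. That is true. Residents are nested in teams as well, so clustering reaches the primary knowledge outcome, while the detection note does not.

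**Conclusion.** The concern holds for patient-level or reading-level analysis. The allocation unit in Section 3 and the methods in Section 8 do not match, and nothing in the documents bridges the gap. Given positive correlation within team beyond centre, precision will generally be overstated. The size is illustrative: 6.0-32.1% true error at nominal 5% with no centre variance, and about 4.8-29.5% if centre explains 10%. All of it rests on assumed team sizes, ICCs and centre shares.

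The undefined unit and denominator are missing detail. They become a possible source of bias only if a yes/no is used and testing or stay differs by arm, and then in an uncertain direction. The change is one the sponsor should make. Confidence is medium, because the number of teams, their size and the ICC are unknown.

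**What to change.** **Main change.** Analyse both glycaemic outcomes with a method that accounts for the randomised team (and for patient, if readings are the unit) and for centre. Add a small-sample correction if teams are few. A mixed model, GEE or an analysis of team summaries would each do. The same team term should be considered for the other outcomes in Section 8, including knowledge.

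**Secondary change.** State the unit and denominator. Where reading counts are available, report the per-patient proportion of readings out of range, with tests per patient-day and length of stay by arm, rather than rely on an unadjusted yes/no alone. Rules for repeat readings, an offset for number of readings, or a scheduled-readings analysis are optional.

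**Cost.** The clustering change needs only team and centre identifiers and SAP wording. On the assumed inputs with no centre variance, intervals widen by √1.09 = 1.04 to √3.90 = 1.97. Few teams add more through the t critical value:

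- 4 teams per arm, no centre term: t(6) = 2.447, and 2.447/1.96 = 1.25.
- 8 teams per arm, no centre term: t(14) = 2.145, giving 1.09.
- 4 teams per arm in a team-level analysis adjusted for centre: 1.31 with two centres (t(5) = 2.571) and 1.42 with three (t(4) = 2.776).

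The documents are written in the past tense and do not say that reading counts were abstracted. The clustering change may therefore be a documented re-analysis, and the proportion measure may require reopening charts.

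### The hyperglycaemia outcome has no start of counting, so glucose already above 180 mg/dL on arrival would be scored as an event and dilute the difference between groups

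*Combined protocol and SAP*

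**What the plan says.** Section 6 lists among the secondary outcomes "Incidence of hyperglycemia (>180 mg/dL) and hypoglycemia (<70 mg/dL" and adds nothing on when counting begins or ends, how a value present at admission is treated, or whether the unit is the patient, the patient-day or the reading. The matching objective in Section 2 is "To evaluate the effect on the occurrence of hypoglycemia and hyperglycemia during hospitalization". Section 1 gives the broader aim as including "the prevention and management of glycemic extremes during hospitalization".

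Section 3 says the patient data come from "a retrospective chart review of hospitalized patients cared for by the participating teams", and that "Internal medicine clinical teams were block-randomized using stratified allocation by center". It gives no review window and no patient eligibility rule.

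Section 8 has no analysis specific to this outcome. Its general rule is "Categorical variables were analyzed using Pearson's chi-square test or Fisher's exact test, as appropriate". It also provides for a logistic regression to identify predictors, "including variables with clinical relevance or $p < 0.20$ in the univariate analysis". Admission glucose is not named anywhere.

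**The concern.** The intervention reaches patients only through what the trained residents order and monitor. A glucose above 180 mg/dL on arrival describes the patient's state before that care could have any effect. If it counts as an event, it counts alike in both groups whatever the residents learned.

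High arrival values are plausible here. The trial's title places it in patients with hyperglycaemia and diabetes, and Section 1 reports that about half of the diabetes cases in one Brazilian study had been undiagnosed. The documents do not say how common such values are at admission.

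Under a patient-level any-event count, a patient who arrives at 300 mg/dL and is controlled from day 2 scores the same as one uncontrolled throughout. Good management of a high arrival value, which is part of the stated aim, would then be invisible. The comparison would be pulled towards no difference, and chance imbalance in arrival glucose between the groups would enter the outcome directly.

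**Working it through.** **The plan's own figure.** The only sample-size figure is 62 questionnaires, in Section 7: "Based on previous data showing 46.44% accuracy in key knowledge items", rising to 80%, with 80% power at 5%. It reproduces: the pooled two-sided two-proportion formula gives 32 per group (64 in total) and the arcsine formula gives 31 per group (62). It concerns the knowledge outcome. The plan has no figure for hyperglycaemia, so what follows is illustrative.

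**Inputs, all assumed.** Hyperglycaemia after admission: 50% in control, 35% with the intervention. Share *a* already above 180 mg/dL at admission: 0 to 70%. Admission readings independent of later ones. Patients independent (clustering by team ignored).

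**Patient-level any-event outcome.** Whole-stay risk = a + (1 − a) × p, where p is the later risk. The difference is therefore (1 − a) × (p_control − p_intervention).

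Patients per arm = (1.960 + 0.842)² × [P1(1 − P1) + P2(1 − P2)] / (P1 − P2)², with (1.960 + 0.842)² ≈ 7.849 (two-sided 5%, 80% power, unpooled variance). For a = 20%: 7.849 × (0.2400 + 0.2496) / 0.12² = 266.9, so 267.

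| Share high at admission | Control | Intervention | Difference (points) | Patients per arm |
|---|---|---|---|---|
| 0% | 50.0% | 35.0% | 15.0 | 167 |
| 20% | 60.0% | 48.0% | 12.0 | 267 |
| 30% | 65.0% | 54.5% | 10.5 | 339 |
| 50% | 75.0% | 67.5% | 7.5 | 568 |
| 70% | 85.0% | 80.5% | 4.5 | 1,103 |

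At an assumed 200 patients per arm (pooled formula), power is 86% with a = 0, 67% with a = 20% and 47% with a = 40%.

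**If independence fails.** Let a = 50%, with later hyperglycaemia in control of 70% among those high at admission and 30% among the rest, so still 50% overall.

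- Proportional effect (every risk × 0.7, giving 49% and 21%, or 35% overall): whole-stay risk is 0.5 + 0.5 × 0.30 = 65.0% versus 0.5 + 0.5 × 0.21 = 60.5%, a difference of 4.5 points.
- Uniform 15-point effect: 65.0% versus 0.5 + 0.5 × 0.15 = 57.5%, a difference of 7.5 points.

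The result depends on how the effect is spread across patients.

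**Reading-level outcome.** With m readings per patient, one of them the admission reading, the share of the effect retained is (m − 1)/m: 75% for m = 4, 92% for m = 12 and 96% for m = 28.

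**The case against.** The strongest reply is that the documents never state a whole-stay rule. Section 6 gives thresholds, Section 2 gives a period, and incidence can mean new events, which would leave out values present at arrival. A reader might infer that the plan deliberately scores admission readings; the text does not go that far. What stands against the reply is that Section 2 speaks of occurrence over the hospitalisation, which in its ordinary sense begins at admission, and nothing tells a chart reviewer to leave arrival values out. If new events were meant, the plan needs to say so.

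A reader might also infer that any effect of the intervention would be hidden, or that the damage is the same whatever the unit of analysis. Neither is supported. A difference remains in every scenario above, and a reading-level measure with many readings loses little. The missing unit is thus part of the same gap. Nor do the documents give a number of teams, so an argument resting on few teams has no basis in them.

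Section 8 would allow admission glucose into the logistic model as clinically relevant. That is a permission, not a plan. Adjustment would also address imbalance at arrival without removing arrival events from the outcome.

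Finally, part of the first day is the team's own work, and the stated aim covers management as well as prevention. That is a fair argument against making a 24-hour exclusion the main rule. It weighs more heavily for hypoglycaemia, where such a cut would drop low readings after the team's first insulin orders, although insulin prescribing is itself a target of the trial.

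**Conclusion.** The point holds as a gap in the outcome definition with a predictable direction. With no start of counting, hyperglycaemia present on arrival would be scored as an event in both groups, and the stated comparison does not adjust for it. The consequence is dilution.

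For a patient-level any-event outcome with independent admission readings, the absolute difference is multiplied by (1 − share high at admission). The assumed 15 points falls to between 12 and 4.5 as that share goes from 20% to 70%. The rates and the share are assumptions, because the documents give neither. Clustering by team, ignored here, would raise all the patient numbers.

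The point concerns hyperglycaemia, one of several secondary outcomes. It leaves the primary knowledge outcome and its figure of 62 untouched and gives no reason to discard early hypoglycaemia. The change is worth making because it costs little.

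**What to change.** **Section 6.** Start counting hyperglycaemia after the first (admission) glucose, once the patient is under the randomised team's care. State when counting ends, and state the unit of analysis and its denominator. Keep hypoglycaemia on the first day, after the team takes over, as an outcome.

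**Section 8.** Adjust the between-group hyperglycaemia comparison for the first admission glucose taken from the chart, named in advance instead of left to the p < 0.20 screen. Report whole-stay occurrence descriptively. Add a later start, such as 24 hours, as a sensitivity analysis for hyperglycaemia: a second reading taken soon after arrival may still reflect the presenting state, and this shows how much that matters.

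**Cost.** A few sentences, and use of reading times, which should be in the charts under review, although the documents do not confirm this. No new patients are needed. Patients with only one reading contribute no hyperglycaemia outcome, and their number should be reported by group. The design is written in the past tense, so if results are already known, the change should be labelled post hoc.
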